The investigator is responsible for ensuring that all disease-related events observed by the investigator or reported by the subject that occur after randomization through EOS/safety follow-up visit, or 30 days after the last administration of IP, whichever is later are reported on the Event CRF as disease related.

Disease-related events assessed by the investigator to be more severe than expected and/or related to the investigational medicinal product(s)/study treatment/protocol-required therapies and determined to be serious must be recorded on the event CRF as serious adverse events. Additionally, the investigator is required to report a fatal disease-related event on the Event CRF as a disease-related event.

Section: 9.2.2.1 Reporting Procedures for Adverse Events That Do Not Meet Serious Criteria

First paragraph, add:

Adverse events possibly related to study procedures, adverse device effects and serious adverse events are reported from signing of the ICF. All other adverse events are reported from the time of randomization.

Protocol Number: 20130286 Page 19 of 20

Date: 30 January 2017

Product: Evolocumab

Replace:

The investigator is responsible for ensuring that all adverse events observed by the investigator or reported by the subject that occur after randomization through EOS/safety

follow-up, or 30 days after the last administration of IP, whichever is later, are reported

using the Event CRF.

With:

The investigator is responsible for ensuring that all adverse events observed by the investigator or reported by the subject that occur from signing of the ICF or from the time of randomization through the EOS/safety follow-up, or 30 days after the last administration of IP, whichever is later, are reported using the event CRF.

Fourth and fifth paragraphs, add last sentence:

Relatedness means that there are facts or reasons to support a relationship between investigational product and the event.

Section: 9.2.2.2 Reporting Procedures for Serious Adverse Events

Third paragraph, replace:

The investigator may be asked to provide additional follow-up information, which may include a discharge summary or extracts from the medical record. Information provided about the serious adverse event must be consistent with that recorded on the Event CRF.

With:

The investigator may be asked to provide additional follow-up information, which may include a discharge summaries, medical records, or extracts from the medical record. Information provided about the serious adverse event must be consistent with that recorded on the Event CRF.

Section: 9.3 Pregnancy and Lactation Reporting

Replace:

If a pregnancy occurs in a female subject, or female partner of a male subject, while the subject is taking protocol-required therapies report the pregnancy to Amgen as specified below.

Protocol Number: 20130286 Page 20 of 20

Date: 30 January 2017

Product: Evolocumab

With:

If a pregnancy occurs in a female subject, or a male subject fathers a child, while the subject is taking evolocumab/placebo, report the pregnancy to Amgen Global Patient

Safety as specified below.

Add fourth paragraph:

If a female subject becomes pregnant during the study, the investigator should attempt to obtain information regarding the birth outcome and health of the infant. If the outcome of the pregnancy meets a criterion for immediate classification as a serious adverse event (eg. female subject experiences a spontaneous abortion,

stillbirth, or neonatal death or there is a fetal or neonatal congenital anomaly), the

investigator will report the event as a serious adverse event.

Sixth paragraph, replace:

In addition to reporting a lactation case during the study, investigators should monitor lactation cases that occur after the last dose of protocol-required therapies through

15 weeks after the end of treatment with evolocumab/placebo.

With:

In addition to reporting a lactation case during the study, investigators should report lactation cases that occur after the last dose of protocol-required therapies through 15 weeks after the end of treatment with evolocumab/placebo.

Add eighth paragraph:

If a male subject's female partner becomes pregnant, the investigator should discuss obtaining information regarding the birth outcome and health of the infant

from the pregnant partner.

Section: 10.1.3 Covariates and Subgroups

Add:

Section: Appendix B, Sample eSerious Adverse Event Contingency Report Form

Replaced form with current version

		10.6.2	Laborator	y Test Results	28
		10.6.3	Vital Signs	S	28
		10.6.4	Antibody I	Formation	28
		10.6.5	Exposure	to Investigational Product	28
		10.6.6	Exposure	to Other Protocol-specified Treatment	29
11.	Chan	ges From	Protocol-spe	ecified Analyses	29
12.	Litera	ture Citati	ons / Refere	ences	30
13.	Apper	ndices			31
				List of Tables	
Tabl	le 1. Im	putation	Rules for Inc	complete Dates	19
		•		· Summary Table	
				List of Figures	
Figu	re 1. M	Multiplicity	Adjustment	Methods	21
90	· · ·				
۸	ondis A	Analytis	od Chuduuss	List of Appendices	0.0
				ek Assignments	
				ogy Criteria for AEs (CTCAE)	
App	endix C	. Framing	gham Risk S	Score (FRS)	34

Statistical Analysis Plan: 20130286 Date: 20 January 2019 Page 4 of 35

Table of Abbreviations

Abbreviation or Term	Definition/Explanation
ACC	American College of Cardiology
AE	Adverse event
AHA	American Heart Association
Al	Autoinjector
ALP	Alkaline phosphatase
ALT	Alanine aminotransferase
AMD	Automated mini-doser
ApoA1	Apolipoprotein A-I
АроВ	Apolipoprotein B
AST	Aspartate aminotransferase
BP	Blood pressure
CAS	Completer analysis set
CD4	Cluster of differentiation 4
CHD	Coronary heart disease
СК	Creatine kinase
СМН	Cochran Mantel-Haenszel
CRF	Case report form
CSR	Clinical Study Report
CTCAE	Common Terminology Criteria for Adverse Events
DMC	Data Monitoring Committee
DQR	Data Quality Review
eCRF	Electronic Case Report Form
EOIP	End of Investigational Product
End of Study (end of trial)	Defined as the date when the last subject has completed all planned
End of Olday (Cha of thai)	study procedures up to and including the visit as outlined in the Schedule of Assessments
End of Study (Primary completion)	The date when the last subject has completed the assessments for week 24
End of Study for Individual Subject	Defined as the last day that protocol-specified procedures are conducted for an individual subject
End of Treatment	Defined as the last assessment for the protocol-specified treatment phase of the study for an individual subject

Product: Evolocumab Statistical Analysis Plan: 20130286 Date: 20 January 2019 Page 5 of 35

Abbreviation or Term	Definition/Explanation
EOS	End of study
FAS	Full analysis set
FRS	Framingham Risk Score
GSO-DM	Global Study Operations-Data Management
HbA1c	Hemoglobin A1c
HCV	Hepatitis C virus
HDL-C	High-density lipoprotein cholesterol
HIV	Human immunodeficiency virus
ICF	Informed consent form
ICH	International Conference on Harmonisation
IP	Investigational product
IPDs	Important Protocol Deviations
IVRS	Telecommunication technology that is linked to a central computer in real time as an interface to collect and process information.
LAS	Long-term analysis set
LDL-C	Low-density lipoprotein cholesterol
LDLR	Low-density lipoprotein receptor
LFT	Liver function test
LH	Luteinizing hormone
Lp(a)	Lipoprotein(a)
MedDRA	Medical Dictionary for Regulatory Activities
МІ	Myocardial infarction
PI	Protease inhibitor
QM	Once monthly
sc	Subcutaneous
SD	Standard deviation
Study day 1	Defined as the first day that protocol-specified investigational product(s)/protocol required therapies is/are administered to the subject
TBL	Total bilirubin
TC	Total Cholesterol
TEAE	Treatment Emergent Adverse Event
ULN	Upper limit of normal

Statistical Analysis Plan: 20130286

Abbreviation or Term	Definition/Explanation
VLDL-C	Very low-density lipoprotein cholesterol
WHODRUG	World Health Organization Drug

Statistical Analysis Plan: 20130286

Date: 20 January 2019 Page 7 of 35

1. Introduction

The purpose of this Statistical Analysis Plan (SAP) is to provide details of the statistical analyses that have been outlined within the protocol amendment 1 for Evolocumab Study 20130286 dated 30 January 2017. The scope of this plan includes the primary analysis and final analysis that are planned and will be executed by the Biostatistics department unless otherwise specified.

2. Objectives

2.1 Primary

To evaluate the effect of 24 weeks of subcutaneous (SC) evolocumab administered every month (QM) compared with placebo QM on percent change from baseline in low-density lipoprotein cholesterol (LDL-C) in human immunodeficiency virus (HIV)-positive subjects with hyperlipidemia or mixed dyslipidemia

2.2 Secondary

- To assess the effects of 24 weeks of SC evolocumab QM compared with placebo QM on change from baseline in LDL-C, and percent change from baseline in non-high-density lipoprotein cholesterol (non-HDL-C), apolipoprotein B (ApoB), total cholesterol (TC), lipoprotein(a) [Lp(a)], triglycerides, HDL-C, and very low-density lipoprotein cholesterol (VLDL-C), in HIV-positive subjects with hyperlipidemia or mixed dyslipidemia
- To assess the effects of 24 weeks of SC evolocumab QM compared with placebo QM on percent of subjects attaining LDL-C < 70 mg/dL (1.8 mmol/L) in HIV-positive subjects with hyperlipidemia or mixed dyslipidemia
- To assess the effects of 24 weeks of SC evolocumab QM compared with placebo QM on percent of subjects attaining a 50% reduction in LDL-C from baseline in HIV-positive subjects with hyperlipidemia or mixed dyslipidemia

2.3 Safety

To evaluate the safety and tolerability of SC evolocumab QM compared with placebo QM in HIV-positive subjects with hyperlipidemia or mixed dyslipidemia

2.4 Exploratory

Statistical Analysis Plan: 20130286

Date: 20 January 2019 **Page 8 of 35**

3. Study Overview

3.1 Study Design

This is a phase 3b, multicenter, double-blind, randomized, placebo-controlled study with an open-label extension period designed to assess the efficacy and safety of evolocumab in HIV-positive subjects with hyperlipidemia and/or mixed dyslipidemia. Treatment with baseline HIV and lipid-lowering (if applicable) medications being taken at randomization will continue throughout the clinical study. The study consists of 3 periods:

- Screening (to ensure tolerance of SC injections, includes a placebo injection)
- Double-blind treatment period
- Open-label extension period

Subjects will undergo screening procedures, including laboratory assessments and a screening placebo injection, before being randomized 2:1 into the following treatment groups for the double-blind treatment period:

- SC evolocumab 420 mg QM
- SC placebo QM

The overall sample size will be approximately 450 subjects, with approximately 300 subjects in the evolocumab group. Randomization will be stratified by entry statin treatment (yes/no) and hepatitis C status (yes/no). The size of the subgroup not on statin therapy is expected to be approximately 10% and no more than 20% of the subjects. This enrollment projection is expected to be reflective of clinical practice.

The double-blind treatment period will be 24 weeks, after which subjects who received a dose of investigational product (IP) at week 20 will continue in an open-label period during which all subjects will be treated with QM evolocumab. The open-label period will continue up through the end of study (EOS) visit at week 52.

SC evolocumab and placebo will be administered QM at the study site or appropriate non-investigator site settings (eg, at the subject's home) by automated mini-doser (AMD) or by spring-based prefilled autoinjector/pen (AI/Pen).

Statistical Analysis Plan: 20130286

Date: 20 January 2019 **Page 9 of 35**

3.2 Sample Size

The planned sample size for the comparison between evolocumab 420 mg QM and placebo at a ratio of 2:1 in the double-blind treatment period is 450 total subjects.

The primary analysis will require the 2-sided tests of the primary endpoint to be significant at a level of 0.05. The planned sample size should provide adequate power to determine the superiority of evolocumab 420 mg QM relative to placebo as measured by the primary endpoint. From the integrated efficacy analysis of completed phase 3 studies, the treatment effect of evolocumab 420 mg QM compared to placebo and the corresponding 95% confidence interval at the mean of weeks 10 and 12 was -64.98% [-69.51%, -60.45%], with treatment effect ranges between -55.1% and -62.33% from Studies 20110114, 20110115, and 20110117. The assumed treatment effect between the primary endpoint in evolocumab 420 mg QM is 40%, with a common standard deviation (SD) of 20%. This SD assumption is based on evolocumab phase 3 results.

This sample size will provide approximately 99% power for the primary endpoint in testing the superiority of evolocumab dose regimen over placebo, assuming a dropout rate of 10%.

In addition, 300 subjects in the evolocumab 420 mg QM group will provide approximately 95% probability of detecting adverse events that occur at a rate of 1%.

It is expected that the proportion of subjects assigned to the no statin use at baseline stratum will be approximately 10%. In this stratum, 30 subjects in the evolocumab 420 mg QM group will provide approximately 79% probability of detecting adverse events that occur at a rate of 5%.

4. Study Endpoints and Covariates

4.1 Study Endpoints

4.1.1 Primary efficacy endpoint

Percent change from baseline in LDL-C at week 24

4.1.2 Secondary efficacy endpoints

For week 24 the following secondary endpoints will be characterized:

- Tier 1
 - Change from baseline in LDL-C
 - Percent change from baseline in non-HDL-C
 - Percent change from baseline in ApoB
 - Percent change from baseline in TC

Statistical Analysis Plan: 20130286

[figure not shown]
Date: 20 January 2019 **Page 10 of 35**

- Achievement of target LDL-C <70 mg/dL (1.8 mmol/L)
- LDL-C response (50% reduction of LDL-C from baseline)
- Tier 2
 - Percent change from baseline in Lp(a)
 - o Percent change from baseline in triglycerides
 - Percent change from baseline in HDL-C
 - o Percent change from baseline in VLDL-C

4.1.3 Safety endpoints

- Subject incidence of treatment emergent adverse events
- Safety laboratory values and vital signs at each scheduled assessment
- Incidence of anti-evolocumab antibody (binding and neutralizing) formation

4.1.4 Exploratory endpoints

Statistical Analysis Plan: 20130286

Date: 20 January 2019 Page 11 of 35

4.2 Planned Covariates

Baseline covariates include:

- Stratification factors in Double-blind Treatment Period:
 - Statin use at baseline (yes/no)
 - Hepatitis C status (yes/no)
- Age
- Sex
- Race (black, white, and other)
- LDL-C
- Family history of premature coronary heart disease (yes/no)
- •
- Region (North America, Europe, other)
- Body Mass Index (BMI)
- Glucose tolerance status (type 2 diabetes mellitus, metabolic syndrome, neither type 2 diabetes mellitus nor metabolic syndrome)
- Hypertension (yes, no)
- Current smoker (yes, no)
- Baseline CHD risk factors ≥ 2 (yes, no)
- Triglycerides
- NCEP high risk (yes, no)
- Statin intensity (High/Moderate/Low intensity as per ACC/AHA guidelines)
- Lipid entry target (above both non-HDL-C and LDL-C entry criteria thresholds, above non-HDL-C entry criteria threshold only, and above LDL-C criteria threshold only)
- Protease inhibitor use

5. Hypotheses and/or Estimations

The null hypothesis is that there is no mean difference in the mean percent change from baseline at week 24 in LDL-C between evolocumab 420 mg QM and placebo, and the alternative hypothesis is that a mean difference does exist.

6. Definitions

6.1 Study Time Points

Enrollment Date

Enrollment Date is the same as randomization date (ie, the date a subject is randomized in the interactive voice response system (IVRS) as recorded on the eCRF).

Statistical Analysis Plan: 20130286

Study Day 1

For each subject, Study Day 1 is defined as the first day of investigational product administration (SC evolocumab 420 mg QM or SC placebo QM). If a subject enrolled but never received IP, Study Day 1 is defined as the enrollment day.

Study Day

For each subject, and for a given date of interest, study day is defined as the number of days since Study Day 1:

Study day = (date of interest – Study Day 1 date) + 1.

If the date of interest is prior to the Study Day 1:

Study day = (date of interest – Study Day 1 date), so that the day prior to Study Day 1 is study day -1.

First Dose Date of SC IP (TR01SDTM)

For each subject, the first dose date of SC IP is defined as the first date of investigational product administration, equivalent to study day 1.

First Dose Date of SC IP in the Open-label period (TR02SDTM)

For each subject, the first dose date of SC IP in the open-label period is defined as the first date of open-label investigational product administration.

Last dose date of Double-blind Investigational Product

For each subject, the last dose date of double-blind investigational product is defined as the date of the last administration of double-blind investigational product.

End of Investigational Product (EOIP) Date

For each subject, the end of investigational product date is defined as the date of decision to end investigational product.

End of Study (EOS) Date

For each subject, the End of Study Date is the date recorded on the End of Study eCRF.

6.2 Demographics and Baseline Related Definitions

Age

Subject age at enrollment will be collected in years in the clinical database.

Statistical Analysis Plan: 20130286

Date: 20 January 2019 **Page 13 of 35**

Baseline Lipid and Lipid-related Parameters

Baseline values for fasting lipids (total cholesterol, HDL-C, LDL-C, VLDL-C and triglycerides), ApoA1, ApoB, Lp(a) and their derived parameters (eg, ratio between them) are defined as the mean of the two most recent non-missing fasting concentrations measured through central lab prior to or on Study Day 1. If for any reason only 1 value is available, then that value will be used as baseline.

Other Baseline Values

The baseline value is defined as the last non-missing value collected prior to or on Study Day 1.

Change (absolute change) from Baseline

The arithmetic difference between a post-baseline value and baseline for a given time point:

Change (absolute change) from baseline = (post-baseline value – baseline value)

Percent Change from Baseline

The percent change from baseline for a given variable at a given time point is defined as:

100 x [(value at given time point – baseline value) / baseline value]

Baseline Metabolic Syndrome

For each subject without type 2 diabetes mellitus, metabolic syndrome is identified by the presence of 3 or more of the components listed below (modified AHA/NHLBI criteria). Subjects with type 2 diabetes cannot be categorized as having metabolic syndrome.

Risk Factor	Defining Level
Elevated waist circumference:	
Non-Asian:	
Men	≥ 102 cm
Women	≥ 88 cm
Asian:	
Men	≥ 90 cm
Women	≥ 80 cm
Triglycerides	≥ 150 mg/dL
HDL cholesterol	
Men	< 40 mg/dL
Women	< 50 mg/dL
Blood Pressure	SBP ≥ 130 mmHg or DBP ≥ 85 mmHg
	OR Hypertension checked 'yes' on
	Cardiovascular Medical History eCRF
Fasting glucose	≥ 100 mg/dL

Statistical Analysis Plan: 20130286

Date: 20 January 2019 Page 14 of 35

Baseline CHD Risk Factors

A subject will be categorized as having 2 or more CHD Risk Factors (Y/N) from the list of the modified NCEP ATP III risk factors:

- current cigarette smoking
- hypertension
- type II diabetes mellitus
- family history of premature CHD as recorded on the Cardiac Risk Factors eCRF
- low HDL-C defined as baseline HDL-C < 40 mg/dL in men and < 50 mg/dL in women.

Baseline National Cholesterol Education Program (NCEP) Risk Categories

Risk Factor	Defining Level	
High Risk: CHD or CHD Risk Equivalent	Coronary Artery Disease OR Cerebrovascular or Peripheral Vascular Disease OR Type 2 Diabetes Mellitus OR 2 or more Risk Factors (see below) AND FRS > 20% (see Appendix C for FRS calculation)	
Moderately High Risk	NOT High Risk AND 2 or more Risk Factors AND FRS ≥ 10% AND ≤ 20%	
Moderate Risk	NOT High Risk AND 2 or more Risk Factors AND FRS < 10%	
Lower Risk	NOT High Risk AND 0 to 1 Risk Factor	

Risk Factors for NCEP Risk Categories:

Risk factors are: current cigarette smoking, hypertension or (baseline SBP \geq 140 or DBP \geq 90 mmHg), family history of premature CHD as recorded in the Cardiac Risk Factors eCRF form, low HDL-C cholesterol defined as baseline HDL-C < 40 mg/dL, age \geq 45 years in men or \geq 55 years in women.

Systematic Coronary Risk Estimation (SCORE) Categories

The SCORE system estimates the 10-year risk of a first fatal atherosclerotic event, whether heart attack, stroke, or other occlusive arterial disease, including sudden cardiac death (ESC/EAS 2011). The SCORE risk estimates will be computed from the

Statistical Analysis Plan: 20130286

Date: 20 January 2019 Page 15 of 35

high and low risk region tables based on sex and baseline smoking status, systolic blood pressure, total cholesterol and age.

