7.1 Schedule of Assessments

Product: Evolocumab

Screening assessments and study procedures are outlined in this section and in Table 3 (Schedule of Assessments).

Product: Evolocumab
Protocol Number: 20130286
Date: 30 January 2017

Date: 30 January 2017 Page 33 of 73

Table 3. Schedule of Assessments

		Double-Blind Period				Open-Label Period		
Study Day / Timepoint	Screening 4 (± 1) weeks	Day 1	Week 12 ± 3 days	Week 20 ± 3 days	Week 24 ± 3 daysª	Week 36 ± 7 days	EOS Week 52 ± 7 days	
General Procedures								
Informed consent	Х							
Medical history	Х							
Vital signs	Х	Х	Х	Х	Х	Х	Х	
Safety data reporting ^b	Х	Х	Х	Х	Х	Х	Х	
Concomitant therapy	Х	Х	Х	Х	Х	Х	Х	
Physical exam	Х	Х			Х		Х	
Body weight, waist circumference	Х				Х		Х	
Body height	Х							
Screening placebo injection ^c	Х							
Randomization		Х						
Central Laboratory								
Fasting lipids, ApoA1, ApoB, Lp(a)	X	Х	Х		Х	Х	Х	
		Х	Х		Х	Х	Х	
		Х	Х		Х	Х	Х	
HIV viral load and CD4	Х	Х	Х		Х	Х	Х	
Hepatitis C antibodies	X							
Hepatitis C viral load ^d	Х	Х	Х		Х	Х	Х	
Chemistry	X	Х	Х		Х	Х	Х	

Page 1 of 2

Footnotes defined on next page of this table

Product: Evolocumab
Protocol Number: 20130286

Date: 30 January 2017 Page 34 of 73

Table 3. Schedule of Assessments

		Double-Blind Period				Open-Label Period	
Study Day / Timepoint	Screening 4 (± 1) weeks	Day 1	Week 12 ± 3 days	Week 20 ± 3 days	Week 24 ± 3 days ^a	Week 36 ± 7 days	EOS Week 52 ± 7 days
Urinalysis	Х	Х	Х		Х	Х	Х
Hematology	Х	Х	Х		Х	Х	Х
Serum pregnancy, ^e urine pregnancy , ^e FSH/LH/estradiol ^f	Х	Х	х	х	х	х	Х
HbA1c	Х		Х		Х	Х	Х
Biomarkers (blood)		Х	Х		Х		X
Anti-evolocumab antibodies		Х	Х		Х	Х	Х
Investigational Product							
IP dispensing		Х	Х		Х	Х	
IP reconciliation			Х	Х	Х	Х	Х
IP administration (every 4 weeks) ^g		Х	х	Х	Х	Х	

Page 2 of 2

ApoA1=apolipoprotein A-I; ApoB=apolipoprotein B; CD4=cluster of differentiation 4; EOS=end of study; FSH=follicle-stimulating hormone; HbA1c=hemoglobin A1c; HIV=human immunodeficiency virus; IP=investigational product; LH=luteinizing hormone; Lp(a)=lipoprotein(a);

^a At week 24, final double-blind period assessments will be conducted, and the first dose of open-label study drug will be administered.

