10.1 General Principles

To evaluate efficacy and safety of 24 weeks of evolocumab 420 mg QM compared with placebo, the primary analysis will be performed when all randomized subjects in the double-blind treatment period have either completed all the scheduled study visits in the double-blind treatment period or have early terminated from the study. Data will be locked at each clean snapshot (the primary analysis and final analysis).

Based on the locked snapshot for the primary analysis, efficacy and safety analyses will be performed on FAS unless otherwise specified, and data will be summarized by randomized treatment group. Data occurring after the first dose of open-label evolocumab will be excluded from the primary analysis dataset.

The final analysis will be performed when all subjects have completed all scheduled study visits in the open-label period or have early terminated from the study. Based on the final locked snapshot for the final analysis, long-term efficacy and safety analyses will be performed on LAS and the analyses will be descriptive. Safety endpoints and exploratory endpoints will be evaluated for the open-label period and summarized overall and by treatment in the double-blind period.

Statistical Analysis Plan: 20130286

Page 21 of 35 Date: 20 January 2019

Subject disposition, demographics, baseline characteristics, and exposure to IP will be summarized by treatment group. Summary statistics for continuous variables will include the number of subjects, mean, median, standard deviation or standard error, minimum, and maximum. For categorical variables, the frequency and percentage will be given.

Methods of handling missing data for efficacy endpoints are described below. Missing data will not be imputed for safety endpoints.

Multiplicity Adjustment Method

Methods of adjusting for multiplicity due to multiple endpoints (primary and secondary efficacy endpoints) in order to preserve the familywise error rate at 0.05 are described in Figure 1.

[figure not shown]

Figure 1. Multiplicity Adjustment Methods

Statistical Analysis Plan: 20130286

Date: 20 January 2019 Page 22 of 35

The following method will be used to preserve the family-wise error rate for the primary and secondary endpoints:

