10.6.2 Laboratory Test Results

Descriptive statistics will be provided for actual values and changes from baseline in select laboratory parameters at each protocol-specified scheduled visit. Laboratory analytes are provided in the protocol Table 3. Lab shift tables using the CTCAE v4.03 or later grading will be used for the select analytes of interest, when applicable.

In addition, CK and liver function test (LFT) abnormalities will be assessed by the incidence overall and by visits of the following categories:

- CK > 5 x ULN
- CK > 10 x ULN
- ALT or AST ≥ 3 x ULN
- ALT or AST ≥ 5 x ULN
- Total bilirubin ≥ 2 x ULN
- (ALT or AST ≥ 3 x ULN) and (Total bilirubin ≥ 2 x ULN and ALP < 2 x ULN)

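### With a single Study Day 1 baseline, the open-label laboratory changes and shifts of former placebo subjects include their 24 weeks on placebo

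*SAP*

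**What the plan says.** **Baseline.** SAP 6.2, under other baseline values: "The baseline value is defined as the last non-missing value collected prior to or on Study Day 1". Lipids have their own rule and are not part of this point.

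**Anchor date.** SAP 6.1: "Study Day 1 is defined as the first day of investigational product administration (SC evolocumab 420 mg QM or SC placebo QM". For the placebo arm this is the first placebo dose.

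**Open-label date.** SAP 6.1 also states that "the first dose date of SC IP in the open-label period is defined as the first date of open-label investigational product administration" (TR02SDTM). The text available to us defines no baseline from that date.

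**Laboratory summaries.** SAP 10.6.2: "Descriptive statistics will be provided for actual values and changes from baseline in select laboratory parameters at each protocol-specified scheduled visit". It adds: "Lab shift tables using the CTCAE v4.03 or later grading will be used for the select analytes of interest, when applicable". No separate reference value is named for open-label visits.

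**Open-label presentation.** SAP 10.1: "Safety endpoints and exploratory endpoints will be evaluated for the open-label period and summarized overall and by treatment in the double-blind period". These analyses are descriptive and use the long-term analysis set (SAP 7.3), which includes every subject with at least one open-label dose and therefore the former placebo subjects. Protocol 10.4.2 gives the purpose of the final analysis as evaluating long-term safety and efficacy of evolocumab.

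**Assessment at the switch.** Protocol Table 3, footnote a: "At week 24, final double-blind period assessments will be conducted, and the first dose of open-label study drug will be administered". Protocol 7.4 requires blood to be drawn before dosing.

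**The concern.** The open-label period is a one-way switch for the placebo arm. The natural question there is how a subject's laboratory values move after starting evolocumab. A change measured from Study Day 1 does not answer it, because it adds the movement during 24 weeks of placebo to the movement after the switch. A grade shift that arose on placebo and persists would appear at weeks 36 and 52. Opposite movements before and after the switch would partly cancel.

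The overall column has a related problem. It combines subjects measured from a pre-evolocumab value with subjects measured from a pre-placebo value, in an analysis meant to describe long-term evolocumab safety.

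The SAP treats adverse events differently. SAP 6.3 divides treatment-emergent events at the first open-label dose. An abnormality that began on placebo is thus kept out of the open-label adverse events but can still appear in the open-label laboratory change or shift.

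**Working it through.** The plan gives no figure on this point. Its power statement (approximately 99%) concerns the week 24 primary endpoint and uses none of the quantities below.

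**Inputs.** SAP Appendix A puts week 24 at day 169, week 36 at day 253 and week 52 at day 365. Study Day 1 is day 1. Allocation is 2:1 with 450 subjects (SAP 3.2), so about 300 and 150. All visits are taken at their nominal days.

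**Step 1: share of the interval on placebo, former placebo subjects.**
Share = (169 − 1) / (visit day − 1).

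| Visit | Days since Study Day 1 | Days on placebo | Placebo share | Days since switch |
|---|---|---|---|---|
| Week 36 | 253 − 1 = 252 | 168 | 168/252 = 66.7% | 253 − 169 = 84 |
| Week 52 | 365 − 1 = 364 | 168 | 168/364 = 46.2% | 365 − 169 = 196 |

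With a baseline taken just before the first open-label dose, the placebo share is 0% and the intervals are 84 and 196 days.

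**Step 2: HbA1c.** Protocol Table 3 schedules HbA1c at screening but not on day 1, so the baseline is the screening value. Assume it was drawn 3 to 5 weeks (21 to 35 days) before Study Day 1. The share of the week 36 interval that precedes any evolocumab is then (21 + 168)/(21 + 252) = 189/273 = 69.2% to (35 + 168)/(35 + 252) = 203/287 = 70.7%.

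**Step 3: effect on the columns.** With the plan's 10% dropout applied equally to both arms, the long-term set is about 270 + 135 = 405, of whom 135/405 = one third are former placebo subjects. Suppose, for illustration, that a laboratory value drifts by d units on placebo, that nothing changes after the switch, and that former evolocumab subjects do not change. The former placebo column then shows d and the overall column shows d/3:

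- d = 0.5: 0.5 and 0.17
- d = 1: 1.0 and 0.33
- d = 2: 2.0 and 0.67

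The documents give no value for d. The shares in step 1 are shares of time, not sizes of bias.

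**Step 4: which summaries use this baseline.**

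- Laboratory change from baseline (SAP 10.6.2): yes, explicitly.
- CTCAE shift tables (SAP 10.6.2): yes, if the general baseline rule applies, since no other reference is given. The analytes are not named.
- CK, transaminase and bilirubin categories (SAP 10.6.2): no, they are multiples of the upper limit of normal.
- Vital signs (SAP 10.6.3): no, only descriptive statistics by visit are planned.
- Body weight and waist: visit windows in Appendix A, but no safety change-from-baseline summary in SAP 10.6.
- Adverse events and antibodies (SAP 6.3, 10.6.1, 10.6.4): no.

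**The case against.** The strongest reply is that little is lost. The open-label analysis is descriptive, and the comparative safety evidence is the randomised 24-week comparison, for which a Study Day 1 baseline is right in both arms. Former placebo subjects have their own column. Actual values and changes are tabulated at every scheduled visit, so a reader can see the placebo arm's drift to week 24 and compare mean levels before and after the switch. Changes in antiretroviral therapy, one possible cause of drift, are summarised with reasons (SAP 10.6.6). If placebo values do not drift systematically, the mean change is not biased.

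This limits the point but does not remove it. Visit means do not give the within-subject change from the pre-switch value, its spread, or a shift from the pre-switch grade. Those need the week 24 value as reference.

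A second reply concerns the remedy. Replacing the baseline throughout would make the overall column pool 84-day changes (former placebo) with 252-day changes (former evolocumab) at week 36. That objection stands against replacement. It does not apply if the second baseline is added for the former placebo column only.

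A reader might also infer more than the documents support:

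- That vital signs, weight and waist are affected. SAP 10.6 plans no change-from-baseline summary for them.
- That the plan reports placebo-period changes as effects of evolocumab. The SAP calls them changes from baseline and shows them by double-blind arm as well as overall; nothing says they will be labelled or interpreted as drug effects.
- That the Study Day 1 baseline is wrong. Change from study baseline and change from the pre-evolocumab value answer different questions, and both are legitimate.

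**Conclusion.** The point holds for non-lipid laboratory values only. In former placebo subjects, the open-label change from baseline includes the placebo period, which makes up 66.7% of the interval at week 36 and 46.2% at week 52 (somewhat more for HbA1c). The overall column mixes these changes with ones measured from a pre-evolocumab value, for roughly one third of its subjects.

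This rests on four assumptions: visits at nominal days; a 2:1 mix in the long-term set; shift tables that follow the general baseline rule; and no open-label baseline in text that is not visible to us. The size of any distortion in laboratory units cannot be derived from the documents, because it depends on drift during placebo.

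No test, alpha, power or primary conclusion is affected. This is a cheap improvement to descriptive safety tables.

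**What to change.** Add to SAP 6.2 and 10.6.2 an open-label baseline for subjects randomised to placebo: the last non-missing laboratory value collected on or before the first open-label dose date (TR02SDTM) and before that dose.

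Define it by the dose, not by the Appendix A week 24 window. That window runs to day 210, while the switch is scheduled for day 169, so it could admit a post-dose sample. SAP 10.1 excludes data after the first open-label dose from the primary analysis dataset only.

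Then:

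- Present former placebo subjects' open-label laboratory changes and CTCAE shifts from this baseline in their own column, alongside the existing change from study baseline.
- Keep the Study Day 1 baseline for former evolocumab subjects.
- Footnote any overall column built on the study baseline to say that former placebo subjects' changes include 24 weeks of placebo.

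**Cost.** A short SAP addition, one derived baseline flag and table labels. No new data are needed: chemistry, hematology, urinalysis and HbA1c are already scheduled at week 24. The final-analysis laboratory tables would carry two labelled baselines. The former placebo group's open-label intervals (84 and 196 days) would be shorter than the former evolocumab group's (252 and 364 days), so the two columns should not be read as like for like in duration.
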